**Table 4-1 Excluded Diseases and Illnesses**

Body system or disease type	Known conditions excluded
Related to SBS	Ongoing radiation enteritis or the presence of damaged enteral tissue due to radiation enteritis Active celiac disease Refractory or tropical sprue Pseudo-obstruction
Gastrointestinal	Active inflammatory bowel disease that requires chronic systemic immunosuppressant therapy that was introduced or changed during the last 3 months Crohn's disease or other diseases that require biological therapy (eg, anti-tumor necrosis factor or natalizumab) that was introduced or changed in the last 6 months Untreated known pre-malignant or malignant change in upper or lower GI biopsy or polypectomy Known, untreated, polyposis conditions (ie, familial adenomatous polyposis, Peutz-Jeghers syndrome, Turcot syndrome, Juvenile polyposis syndrome, Cowden disease, Bannayan-Riley-Ruvalcaba syndrome, Gardner's syndrome, Cronkhite-Canada syndrome, Eversmeyerous polypius) Intestinal or other major surgery scheduled within the time frame of the study Chronic active pancreatitis or active cholecystitis
Immune	Compromised immune system (eg, acquired immune deficiency syndrome, severe combined immunodeficiency), hypersensitivity or allergies to teduglutide or its constituents or GLP-2
Psychiatric	Alcohol or drug addiction within the previous year Major uncontrolled psychiatric illness
General	Significant active, uncontrolled, untreated systemic diseases (eg, cardiovascular, respiratory, renal, infectious, endocrine, hepatic, or central nervous system)

## 4.4 Subject Withdrawal Criteria

All subjects are free to withdraw from participation in this study at any time, for any reason, specified or unspecified, without prejudice to further treatment. Discontinued subjects will not be replaced.

In all cases, the reason for withdrawal must be recorded in the case report form (CRF) and in the subject's medical records. If the reason is not disclosed, every effort must be made up to establish whether the reason was an AE and, if so, this must be reported in accordance with the procedures described in Section 6.2.1.2. As far as possible, all examinations scheduled for the end-of-study evaluations must be performed on all subjects who participate, but do not complete the study according to the protocol.

### 4.4.1 Events Necessitating Withdrawal from Study

The sponsor or designee should be consulted prior to premature withdrawal of a subject. The occurrence of any of the following events may necessitate premature withdrawal of a subject from the study:

- Development of any of the following Inclusion/Exclusion criteria that would interfere with analysis of the study results (ie, compromise PN/I.V.):
  - Significant active, uncontrolled diseases (eg, cardiovascular, renal, cancer) that would put the subject at any undue risk or prevent completion of the study
  - Major surgical interventions (eg, abdominal, vascular)
  - Crohn's disease flare up
  - Use of any excluded medication
  - Pregnant and lactating women
- Occurrence of a serious adverse event (SAE) thought to be related to study drug and not alleviated by symptomatic treatment
- Unwillingness to continue in the clinical study
- Death of the subject
- Investigator/ Sponsor decision (ie. subject non-compliance with study procedures)

- Significant AE or medical decision that precludes the subject from adhering to study requirements

#### **4.4.2 Re-screening of Subjects**

In the event that a subject withdraws from the study in Stage 1, that subject may be re-screened upon the approval of NPS. A new subject number will be assigned.

Subjects whose urine output cannot be stabilized during the stabilization period after 1 repeated effort may not be rescreened.

### **5 TREATMENTS AND TREATMENT PLAN**

After signing the ICF, the subject will enter Stage 1 of the study, which includes screening, optimization and stabilization. The purpose of this stage is to ensure that all subjects are receiving and tolerating a stable minimal (optimized) level of PN/I.V. volume before treatment with teduglutide. If needed, the subject will enter an 8-week maximum optimization period, during which the PN/I.V. volume will be adjusted stepwise in targeted increments of 10% or more of the previous visit's volume ([Appendix 1](#)). Once the PN/I.V. volume is optimized, the subject will enter a minimum 4-week to 8-week stabilization period.

The aim of the study is to evaluate the efficacy of teduglutide in allowing reductions of PN/I.V. volume to less than the stabilized PN/I.V. level. After completion of the PN/I.V. stabilization period, subjects will enter Stage 2 of the study and receive teduglutide for a 24-week dosing period. The algorithm for the stepwise reduction of PN/I.V. during the dosing period is in [Appendix 2](#).

Stage 3 is the long-term extension portion of the study, which will begin immediately following Stage 2. In Stage 3, subjects can continue teduglutide treatment if deemed appropriate by the investigator. During the extension, the PN/I.V. dosage will be adjusted as described in [Appendix 3](#). Subjects will continue to receive teduglutide 0.05 mg/kg/day for up to 24 months or until regulatory approval and commercial availability of teduglutide in Japan. (After the approval of marketing authorization, the study will continue as a post-marketing clinical study until the market launch.)

Any subject who achieves complete independence from PN/I.V. support (either during optimization or at any time during Stage 2 or 3) will continue to receive teduglutide treatment. If a subject relapses following achievement of PN/I.V. independence, PN/I.V. support will be re-initiated and the subject will continue receiving teduglutide.

## **5.1 Treatments Administered**

Teduglutide 0.05 mg/kg/day will be administered daily at home by the subjects, who will self-administer the study drug by SC injection into either thigh or arm or one of the 4 quadrants of the abdomen.

### **5.1.1 Identification of Investigational Product**

Teduglutide for SC injection is provided as a lyophilized powder that must be reconstituted using 0.5 mL sterile water for injection, and used within 5 minutes of reconstitution. The Injection Instruction Leaflets will be provided separately. Each 3.0 mL vial contains 5 mg of teduglutide.

Active ingredient:	teduglutide
Added ingredients:	L-histidine, mannitol, monobasic and dibasic sodium phosphate
Route of administration:	SC injection
Dose:	0.05 mg/kg/day

### **5.1.2 Packaging and Labeling**

Study drug will be packaged, labeled, and delivered to the clinical centers by the sponsor or designee. The study drug kit labeling will include the protocol number, the investigational drug warning, storage conditions, expiry date, drug name or drug code, lot number, sponsor name and country and In-Country Clinical Caretaker name and address. All medication supplied to be used in this study will be manufactured, tested, labeled, and released according to current legal requirements and Good Manufacturing Practice. Ancillary supply kits containing the following will also be provided with the study drug at each visit:

- Pre-filled syringes of sterile water for injection
- Needles to affix to sterile water for injection syringes for reconstitution
- Syringes with needles for injection (dosing)
- Alcohol swabs

### **5.1.3 Storage, Accountability, and Stability**

Study drug will not be dispatched to the center until the sponsor or designee has received all required documents from the study center in accordance with applicable regulatory requirements and relevant standard operating procedures.

The investigator or designee will conduct an inventory upon receipt of the clinical supplies and will acknowledge receipt of the supplies to the sponsor or designee. A copy of the shipping documents must be maintained for the investigator's records. Study drug must be kept in a locked area with access restricted to specific study personnel. Study drug must be stored refrigerated at a temperature between 2 and 8°C (36 to 46°F) until dispensed. Once dispensed to a subject, the study drug and the sterile water diluent should be kept at 15 to 25° C (59 to 77°F). If there are concerns that this temperature cannot be maintained, the study drug may be refrigerated. Therefore, the overall acceptable storage temperature range is 2 to 25°C (36 to 77°F).

Study drug kits will be dispensed to subjects at each of the study visits. Each study drug kit is sufficient for a treatment period of 1 week and enough kits are to be supplied to cover the period until the next planned study visit. Additional study kits will be provided as necessary.

The investigator is to keep a current record of the inventory and dispensing of all clinical supplies. This record will be made available to the sponsor's monitor for the purpose of accounting for all clinical supplies. Any discrepancy or deficiency will be recorded, with an explanation. All supplies sent to the investigator must be accounted for and in no case will clinical supplies be used in any unauthorized situation.

All used and unused study drug vials, including the supplies must be returned by the subjects and retained at the center until instructions are received for return and/or destruction of supplies. Further details will be provided in the study reference manual.

## **5.2 Dose Regimen**

The volume of reconstituted study drug is to be administered at a fixed dose of 0.05 mg/kg. The dose will be calculated as an average of the 2 measurements of body weight at the stabilization and baseline visits. The dose of study drug administered at baseline should be maintained throughout the study period without adjustments for changes in a subject's weight.

### **5.2.1 Selection of Doses in Study**

The dose of teduglutide selected for this study is based on the efficacy and safety results of up to 2 ½ years of treatment in prior studies, as discussed in Section 1.3. Due to the favorable

risk/benefit profile, the teduglutide dose of 0.05 mg/kg/day was chosen as the dose for all adult safety and efficacy studies.

### **5.2.2 Selection and Timing of Dose for Each Subject**

The study drug (teduglutide 0.05 mg/kg/day) will be self-administered immediately after reconstitution by SC injection into 1 of the 4 quadrants of the abdomen or into either thigh or arm. Subjects will be trained to self-inject teduglutide on Day 0. The first SC injection should be administered under the supervision of the investigator or designee and the subject observed for at least 4 hours. Detailed instructions for reconstitution and injection of the study drug can be found in the Injection Instruction Leaflets and the study reference manual. Each day, the injection site should be changed. Subjects with a stoma must avoid using the abdominal quadrant in which the stoma is situated.

The subject should be dosed at approximately the same time each day. If a subject forgets to take drug, that day's dose should be administered as soon as possible, even if this is later in the day or evening. Consecutive doses should be separated by approximately 12 hours.

Dosing must be performed at least 14 hours prior to antibody testing, which will be performed at Baseline and at Weeks 12 and 24 during Stage 2 and at Months 6, 12, 18, and 24 or early termination during Stage 3, or at early termination.

The investigator is responsible for contacting the sponsor or designee prior to interrupting or modifying the subject's daily study drug dosing regimen, ie, as consideration for tolerability issues.

A single discontinuation period of study drug should not exceed 10 consecutive days. Dosage interruptions of study drug are permissible for a maximum of 21 days total per each 24-week period throughout the study.

Dates of days with missed or incomplete doses are to be reported in the diary.

### **5.2.3 Subjects Who Achieve PN/I.V. Independence**

Any subject who achieves complete independence from PN/I.V. support (either during optimization or at any time during the Stage 2 or 3 treatment period) will continue to receive teduglutide treatment. A subject will be considered to have achieved independence from PN/I.V. (completely weaned off PN) if the investigator prescribes no PN and there is no use of PN recorded in the subject diary at the last dosing visit.

If a subject relapses following achievement of PN/I.V. independence, PN/I.V. support will be re-initiated and the subject will continue receiving teduglutide.

## **5.2.4 Compliance with Dosing Regimens**

Subject compliance with study drug dosing will be monitored by the sponsor or designee by counting and examining used and unused vials. In addition, compliance will be checked at every visit by asking the subjects if they have taken their study drug according to instructions and by performing drug accountability.

Compliance is considered to be achieved if the subject has 80% of the planned doses administered.

## **5.3 Prior and Concomitant Medications**

The administration of all medications including concomitant medications (including prescription and nonprescription medications, dietary and nutritional supplements, and vitamins), study drug, and PN/I.V. must be recorded in the appropriate sections of the CRF.

No new medications should be started unless medically necessary and prescribed by the investigator or by another qualified physician involved in the subject's clinical care and who is aware of the subject's study participation.

The mechanism of action of teduglutide may increase absorption of orally administered drugs (eg, motility medication, warfarin, psychotropics, and digoxin), so consideration should be given to modifying concomitant medication regimens. Down-titration of concomitant medication dosages should be considered when drugs, including those with a narrow therapeutic range, are given, especially if given at dosages that are higher than usual.

# **6 STUDY EVALUATIONS AND PROCEDURES**

The objectives of this clinical study are to evaluate the safety, efficacy and pharmacokinetics of teduglutide in Japanese subjects with PN/I.V.-dependent SBS over a 24-week period (Stage 2) followed by a long-term extension (Stage 3) to evaluate safety and continued efficacy.

## **6.1 Efficacy Evaluations**

Reductions in PN/I.V. volume form the basis for most of the efficacy evaluations. The procedures for the stepwise reduction of PN/I.V. during Stages 2 and 3 of this study are given in [Appendix 2](#) and [Appendix 3](#), respectively.

As described in Section [2.1](#), the efficacy endpoints for Stage 2 are as follows:

- Absolute and percent change from baseline in weekly PN/I.V. volume over 24 weeks

- Percentage of subjects who demonstrate a response at Week 20 and again at Week 24.
- Change in days per week of PN/I.V. support
- Changes in plasma citrulline levels from baseline to Week 24 (or EOT)

In Stage 3, absolute and percent change from baseline in weekly PN/I.V. volume and changes in days per week of PN/I.V. support and plasma citrulline levels will continue to be evaluated throughout the long-term extension (see Section 2.2).

Single-dose pharmacokinetics will be evaluated on the first day of teduglutide treatment (Day 0) in Stage 2 only, and pharmacokinetic parameters will be derived as described in Section 2.3.

## 6.2 Safety Evaluations

Safety will be assessed by evaluations of the following variables:

- Adverse events, including GI symptoms
- 12-lead ECGs
- Vital signs, including changes in body weight and BMI
- Laboratory safety data, including electrolyte balance
- Antibodies to teduglutide and ECP. Samples for antibody analysis will be drawn at the start of treatment and at the EOT visit (prior to the administration of teduglutide and at least 14 hours after the previous dose). A 6-month follow-up is planned for any subjects testing positive for teduglutide-specific antibodies following the last dose of study drug.
- Changes in urine output (48-hour oral fluid intake/urine output)
- Abdominal ultrasound
- Upper GI contrast series with small bowel follow-through
- Colonoscopy/sigmoidoscopy of remnant colon
- Physical examinations

### 6.2.1 Adverse Events

During the study, the investigator is responsible for the detection and documentation of any AE or SAE, as defined in this protocol.

### **6.2.1.1 Adverse Event Definition**

An AE is defined as any untoward medical occurrence in a subject or clinical investigation subject administered a pharmaceutical/medicinal product. An AE does not necessarily have to have a causal relationship with this treatment.

An AE can therefore be any unfavorable and unintended sign (including a clinically significant abnormal laboratory finding, for example), symptom, or disease temporally associated with the use of a medicinal product (investigational or marketed), whether or not considered related to treatment with the medicinal product.

An AE includes:

- An exacerbation of a pre-existing illness, sign, symptom, or clinically significant (as determined by the investigator) laboratory test abnormality and clinically significant ECG abnormality
- An illness, sign, symptom, or clinically significant laboratory abnormality that is detected or diagnosed after study drug administration
- Pretreatment or post-treatment events that occur as a result of protocol-mandated procedures

An AE does not include:

- The disease or disorder being studied or signs and symptoms associated with the disease or disorder, unless there is worsening of the condition of the disease or disorder
- A pre-existing disease or condition, present at the start of the study, that does not worsen

## Overdose

Defined as an accidental or intentional administration of an excessive dose of a product, an overdose should be reported to the sponsor using the SAE form. This information will be shared with the NPS Safety Management Team (SMT) and the sponsor's medical monitor.

### 6.2.1.2 Procedures for Reporting Adverse Events

Adverse events may be spontaneously reported by the subject, obtained through nonleading questioning, or noted during examination of a subject. Adverse events will be recorded from the signing of the ICF through the last dose of study drug. Adverse events that are not resolved at the end of study will be monitored with a telephone call by the investigator, as necessary, for approximately 4 weeks after the last dose of study drug or until resolution or until the AE is judged by the investigator to have stabilized.

As they occur, new AEs will be recorded sequentially on the AE page of the CRF. The AE term should note the diagnosis whenever possible, not the individual signs or symptoms (eg, myocardial infarction should be recorded rather than chest pain, elevated cardiac enzymes, and abnormal ECG). Also recorded are:

- Start and stop date and time (date the site becomes aware of the SAE)
- Whether the event is continuing
- Frequency (intermittent, continuous)
- Intensity (mild, moderate, severe)
  - Mild: usually transient, requiring no special treatment and generally not interfering with usual daily activities
  - Moderate: usually ameliorated by simple therapeutic maneuvers and impairs usual activities
  - Severe: requires vigorous therapeutic intervention and interrupts usual activities. Hospitalization may or may not be required.
- Relationship to study drug (not related, related): identify relationship as “related” if a causal relationship between the investigational product and an AE is at least a reasonable possibility
- Whether the AE is serious (ie, an SAE). If identified as an SAE, the AE should be reported on the SAE form according to Section [6.2.2](#) below
- Actions taken (none; study drug dose changed, interrupted, or discontinued; other medication change; nondrug therapy)
- Outcome (resolved, resolved with sequelae, ongoing, fatal). An individual AE receives only one outcome.

Adverse events that are related to study drug and not resolved at the end of treatment will be followed by the site until resolution or until the AE is judged by the investigator to have stabilized.

Laboratory values, blood pressure, ECG evaluations, and clinical findings at the scheduled physical examinations must be reported as AEs if they:

- Are considered clinically significant by the investigator (ie, not part of the subject's medical history),
- Fulfill SAE criteria, and/or
- Cause subject discontinuation from the study.

## **6.2.2      Serious Adverse Events**

An SAE must be recorded on the SAE Form. An SAE requires expeditious handling to comply with regulatory requirements. Any SAEs occurring from the signing of the ICF through 30 days after the last dose of study drug will be captured and must be reported within 24 hours after the investigator is made aware of the event.

### **6.2.2.1    Serious Adverse Event Definition**

An SAE is defined as an AE that results in any of the following outcomes:

- Death
- Is life-threatening. A life-threatening AE is any AE that places the subject – in the investigator's opinion – at immediate risk of death from the reaction as it occurred. It does not include a reaction that, had it occurred in a more serious form, might have caused death.
- Persistent or significant incapacity or substantial disruption of ability to conduct normal life functions
- Hospitalization or prolongation of existing hospitalization
- Congenital anomaly/birth defect
- Important medical events that may not result in death, be life-threatening, or require hospitalization may be considered an SAE when, based upon appropriate medical judgment, they may jeopardize the subject or may require medical or surgical intervention to prevent one of the other outcomes listed in this definition. Examples of such medical events include allergic bronchospasm requiring intensive treatment in an emergency room or at home, blood dyscrasias or convulsions that do not result in hospitalization, or the development of drug dependency or drug abuse.

Scheduled and/or elective hospitalizations occurring under the following circumstances will not be defined as SAEs for this clinical study:

- Planned before entry into the clinical study
- Elective treatment of a condition unrelated to the studied indication or its treatment
- Occur on an emergency, outpatient basis and do not result in admission (unless fulfilling the previous criteria)
- Part of the normal treatment or monitoring of the studied indication and not associated with any deterioration in condition

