##### **4.4.1 Events Necessitating Withdrawal from Study**

The sponsor or designee should be consulted prior to premature withdrawal of a subject. The occurrence of any of the following events may necessitate premature withdrawal of a subject from the study:

- Development of any of the following Inclusion/Exclusion criteria that would interfere with analysis of the study results (ie, compromise PN/I.V.):
  - Significant active, uncontrolled diseases (eg, cardiovascular, renal, cancer) that would put the subject at any undue risk or prevent completion of the study
  - Major surgical interventions (eg, abdominal, vascular)
  - Crohn's disease flare up
  - Use of any excluded medication
  - Pregnant and lactating women
- Occurrence of a serious adverse event (SAE) thought to be related to study drug and not alleviated by symptomatic treatment
- Unwillingness to continue in the clinical study
- Death of the subject
- Investigator/Sponsor decision (ie, subject non-compliance with study procedures)

- Significant AE or medical decision that precludes the subject from adhering to study requirements

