### 6.2.1.1 Adverse Event Definition

An AE is defined as any untoward medical occurrence in a subject or clinical investigation subject administered a pharmaceutical/medicinal product. An AE does not necessarily have to have a causal relationship with this treatment.

An AE can therefore be any unfavorable and unintended sign (including a clinically significant abnormal laboratory finding, for example), symptom, or disease temporally associated with the use of a medicinal product (investigational or marketed), whether or not considered related to treatment with the medicinal product.

An AE includes:

- An exacerbation of a pre-existing illness, sign, symptom, or clinically significant (as determined by the investigator) laboratory test abnormality and clinically significant ECG abnormality
- An illness, sign, symptom, or clinically significant laboratory abnormality that is detected or diagnosed after study drug administration
- Pretreatment or post-treatment events that occur as a result of protocol-mandated procedures

An AE does not include:

- The disease or disorder being studied or signs and symptoms associated with the disease or disorder, unless there is worsening of the condition of the disease or disorder
- A pre-existing disease or condition, present at the start of the study, that does not worsen

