### 6.2.2.1 Serious Adverse Event Definition

An SAE is defined as an AE that results in any of the following outcomes:

- Death
- Is life-threatening. A life-threatening AE is any AE that places the subject – in the investigator’s opinion – at immediate risk of death from the reaction as it occurred. It does not include a reaction that, had it occurred in a more serious form, might have caused death.
- Persistent or significant incapacity or substantial disruption of ability to conduct normal life functions
- Hospitalization or prolongation of existing hospitalization
- Congenital anomaly/birth defect

- Important medical events that may not result in death, be life-threatening, or require hospitalization may be considered an SAE when, based upon appropriate medical judgment, they may jeopardize the subject or may require medical or surgical intervention to prevent one of the other outcomes listed in this definition. Examples of such medical events include allergic bronchospasm requiring intensive treatment in an emergency room or at home, blood dyscrasias or convulsions that do not result in hospitalization, or the development of drug dependency or drug abuse.

Scheduled and/or elective hospitalizations occurring under the following circumstances will not be defined as SAEs for this clinical study:

- Planned before entry into the clinical study
- Elective treatment of a condition unrelated to the studied indication or its treatment
- Occur on an emergency, outpatient basis and do not result in admission (unless fulfilling the previous criteria)
- Part of the normal treatment or monitoring of the studied indication and not associated with any deterioration in condition

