### 6.2.2.2 Procedures for Reporting Serious Adverse Events

All initial and follow-up SAE reports must be reported by the investigator to the sponsor's Global Drug Safety Department and the CRO/Shire Medical Monitor within 24 hours of the first awareness of the event. Note: The 24-hour reporting requirement for SAEs does not apply to reports of abuse, misuse, overdose, or medication errors (see Section 6.2.1.1) unless they result in an SAE.

The investigator must complete, sign, and date the sponsor's Clinical Study Serious Adverse Event and Non-serious AEs Required by the Protocol Form and verify the accuracy of the information recorded on the form with the corresponding source documents (Note: Source documents are not to be sent unless requested) and e-mail the form to the sponsor's Global Drug Safety Department. A copy of the sponsor's Clinical Study Serious Adverse Event and Non-serious AEs Required by the Protocol Form (and any applicable follow-up reports) must also be sent to the sponsor's Medical Monitor using the details specified in the emergency contact information section of the protocol.

Note: Minimum criteria for reporting an SAE are the SAE term, an identifiable subject, a suspect investigational medical product (study drug), and a reporter. Hospitalization is not an AE, but an SAE criterion. The SAE term is the medical event that led to the hospitalization. Surgery is not an AE, but the event that required the subject to have surgery is the SAE term. Death is not an SAE, but an outcome.

Autopsy reports, if applicable, will be forwarded as they become available. All pertinent laboratory results should be entered on the SAE form.

All SAEs must be reported, whether or not they are considered causally related to the study drug. Appropriate clinical, diagnostic, and laboratory measures should be performed to delineate the

cause of the SAE in question and the results reported. Follow-up for the SAE should occur at appropriate intervals until the event/laboratory abnormality:

- Returns to baseline or
- Becomes stable to a clinically acceptable level that is safe for the subject.

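### The SAE definition removes serious status from booked admissions for conditions judged unrelated, even when the condition is new or has worsened since consent

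*Protocol*

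**What the plan says.** The operative text is section 6.2.2.1 of the current, four-stage version of the protocol. The four exemption bullets have the same wording in both three-stage versions.

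- **Seriousness.** One criterion that makes an AE serious is "Hospitalization or prolongation of existing hospitalization".
- **Exemption.** The section then states: "Scheduled and/or elective hospitalizations occurring under the following circumstances will not be defined as SAEs for this clinical study". The first bullet is "Planned before entry into the clinical study". The second is "Elective treatment of a condition unrelated to the studied indication or its treatment". The third covers emergency outpatient attendance that does not lead to admission. The fourth covers routine care or monitoring of the indication, and only where the condition has not deteriorated.
- **AE definition (6.2.1.1).** An AE includes "An illness, sign, symptom, or clinically significant laboratory abnormality that is detected or diagnosed after study drug administration". It also includes an exacerbation of a pre-existing illness.
- **Reporting (6.2.2.2).** "All SAEs must be reported, whether or not they are considered causally related to the study drug". The section adds a naming rule, "Surgery is not an AE, but the event that required the subject to have surgery is the SAE term", and says that assessing causality does not remove the duty to report to the sponsor.
- **Analysis (8.3.1).** SAEs are tabulated twice, overall and treatment-related.
- **Size (4.1).** At least 5 subjects, all treated, with no control arm.

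**The concern.** In this protocol seriousness is otherwise defined by what happens to the subject: death, threat to life, incapacity, hospitalization and so on. Causality is a separate item, assessed afterwards. The second exemption bullet brings a relatedness judgement into the definition itself. For booked admissions, a judgement of unrelated then decides whether the event is serious at all.

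Two things are at stake.

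- **The overall SAE row.** It is meant to be free of causality, with the treatment-related row beside it for the causal view. Under this bullet both rows depend on relatedness.
- **The sponsor's independent view.** Under 6.2.2.2 either the investigator or the sponsor may deem a serious, unexpected event related. If the investigator's judgement makes the event non-serious, no SAE form is sent and that expedited route does not start.

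Long-term safety is a stated objective in section 2. With no comparator, the counts are read at face value.

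**Working it through.** The protocol states no figure on this point, so the check is mainly textual, with one calculation for scale.

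**Step 1. Does the second bullet reach conditions that arise on study?**

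- The first bullet already exempts admissions planned before entry. If the second bullet is to add anything, it must cover admissions arranged after entry.
- The fourth bullet carries its own limit, that there has been no deterioration. The second carries none.
- No other sentence in 6.2.2.1 limits the second bullet to conditions that pre-date consent or are unworsened.

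On its wording, the bullet covers a condition that is new or worse after consent, provided the admission is scheduled or elective and the condition is judged unrelated.

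**Step 2. Follow one case.** A subject develops a new illness during dosing and is booked for elective treatment in hospital.

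| Rule | Result |
|---|---|
| 6.2.1.1, illness diagnosed after dosing | It is an AE |
| 6.2.2.1, hospitalization criterion | It would be an SAE |
| 6.2.2.1, second exemption bullet, condition judged unrelated | Not an SAE through the admission |
| 6.2.2 and 6.2.2.2, 24-hour SAE reporting | Not triggered |
| 8.3.1, overall SAE table | Not counted |
| 6.2.1.2, AE record with relationship to drug | Still recorded |
| 5.3 and 6.2.13, surgical or other treatment on the CRF | Still recorded |

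If the same condition is judged related, the second bullet does not apply and the event remains an SAE. Between the two outcomes only the relatedness judgement differs.

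**Step 3. What the bullet does not touch.** Unscheduled admissions remain SAEs. So do events that are fatal, life-threatening or incapacitating. The important-medical-event criterion stays open, but it is discretionary. In the current version, section 6.2.3 requires 24-hour notice of polyp growth and neoplasia whether or not they are serious, although that does not place them in the SAE table.

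**Step 4. Scale.** Let one subject's only SAE be reclassified. Incidence moves from 1/n to 0/n, a change of 1/n. Exact (Clopper-Pearson) 95% intervals are shown. For 0/n the upper limit is 1 − 0.025^(1/n); at n = 5 this is 1 − 0.478 = 0.522.

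| n | With the event | Without it | Change |
|---|---|---|---|
| 5 (stated minimum) | 1/5 = 20.0% (0.5 to 71.6%) | 0/5 = 0% (0 to 52.2%) | 20 points |
| 10 (assumed) | 1/10 = 10.0% (0.3 to 44.5%) | 0/10 = 0% (0 to 30.8%) | 10 points |
| 15 (assumed) | 1/15 = 6.7% (0.2 to 31.9%) | 0/15 = 0% (0 to 21.8%) | 6.7 points |

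The protocol gives no rate of elective admission and no proportion that would be judged unrelated. The table therefore shows the effect of one such subject, not how often it would happen.

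**The case against.** The strongest reply is that the gap is narrow and little safety information is lost. Much of it stands.

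- **Nothing disappears from the database.** A reader might infer that exempted events vanish before their causality is recorded. They do not. Section 6.2.1.2 records every AE with its relationship to drug, intensity, action and outcome, and 8.3.1 summarizes AEs by relationship and severity. Only the seriousness class changes.
- **There is no outright contradiction.** A reader might set the bullet against 6.2.2.2, or against 4.4.1, where major surgery is a possible reason for withdrawal. But the rule to report all SAEs applies to events already classed as SAEs, the surgery note says how to name the term, and withdrawal is a separate matter from seriousness. All of these can be applied together. What the bullet undercuts is the intent of 6.2.2.2 that reporting should not turn on causality.
- **The most worrying conditions are hard to call unrelated.** A reader might think first of bowel, stoma, biliary or pancreatic disease. In short bowel syndrome, bowel and stoma problems are close to the indication. Section 1.1 describes bile-duct, gallbladder and pancreatic-duct changes as an extension of the drug's pharmacology. The guidance in 6.2.2.2 treats any valid reason for suspicion as enough for related. Applied properly, these would usually not be exempt.
- **One subject may not move the rate.** Section 4.3 allows up to 4 SBS- or PN-related admissions in the year before screening, so a subject may well have another SAE.

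The reply does not answer the main point. For what remains, the wording lets a judgement of unrelated decide seriousness for a condition that is new or worse on study. The important-medical-event route is only discretionary.

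**Conclusion.** The point holds as a defect of definition with limited reach. The second bullet of 6.2.2.1 removes SAE status from booked admissions for conditions judged unrelated, including those that arise or worsen after consent. The direction is known: as written, the rule can only lower the overall SAE count and bypass 24-hour reporting. The frequency is not known and cannot be derived from the protocol.

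The size is 20 percentage points per reclassified subject at n = 5, less with more subjects. This assumes that the subject has no other SAE, that the condition is judged unrelated, and that the important-medical-event criterion is not used.

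The protocol does not support a claim that safety data are lost altogether, that its sections flatly conflict, or that a particular amount of bias is expected. The change is still worth making, because it is cheap and the SAE table of a small uncontrolled study is sensitive to single subjects.

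**What to change.** Amend the second exemption bullet in 6.2.2.1 so that it applies only when three conditions all hold: the condition was present before the ICF was signed, it has not worsened since, and it is unrelated to the studied indication or its treatment. The first two are new; the third is the existing test and should stay. Replacing the unrelatedness test with the other two would newly exempt elective admissions for unworsened conditions that are related to short bowel syndrome.

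With the amendment, this bullet can no longer exempt an admission for a new or worsened condition, and for those events relatedness is recorded only in the causality field. The bullet also lines up with 6.2.1.1, which already leaves unworsened pre-existing conditions outside the AE definition.

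The cost is one sentence in the protocol, a few more SAE forms, and possibly a slightly higher reported SAE rate. It changes a reporting definition, not the care of subjects.
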